### 3.4.5.6 24 Hour Ambulatory Blood Pressure Monitoring

Systolic blood pressure, diastolic blood pressure, pulse pressure and heart rate are collected during the 24-hour ambulatory blood pressure monitoring (ABPM) [REDACTED]. Actual values and changes from baseline values for these four parameters will be summarized using descriptive statistics (including mean, standard deviation, quartiles, median, minima, maxima, and 95% confidence interval) by treatment group at all scheduled study visits. If the scheduled assessment is missing, the recheck measurement closest in time to scheduled visit will be used (if available).

The overall (24 hour) mean for each measure, the day time mean, and the night time mean will be summarized. Appendix A provides more detail of the planned analyses of the 24-hour ABPM data.

### 3.4.5.7 ECG

Actual values for the 12-lead ECGs collected at each visit and changes from baseline in ECG measures (i.e., RR, PR, QRS, QT/QTc interval) at post-baseline visits will be summarized. Additionally, frequency counts for ECG results (normal, abnormal not clinically significant, abnormal clinically significant, or unable to evaluate) will be summarized at each visit. If the scheduled assessment is missing, use the recheck measurement closest in time to scheduled visit (if available).

## 3.5 Analysis of Part 2

All patients in Part 2 will receive an active dose of bardoxolone methyl. Patients must be compliant with dosing and complete Part 1 according to the protocol to be eligible for continuation into the extension period (Part 2). Therefore, separate populations for safety and efficacy will not be defined for Part 2 analyses.

The Part 2 safety and efficacy analyses will be summarized by randomized treatment, pooling all placebo patients and all active patients into various subgroups:

- All PAH patients (Cohorts 1, 2, 3a, and 3b patients)
- All CTD-PAH patients (CTD-PAH patients in Cohorts 1, 2, and 3a)
- All Non-CTD PAH patients (Non-CTD PAH patients in Cohorts 1, 2, and 3b)
- All PH patients (Cohorts 4a, 4b, 4c, 4d)

Due to the ongoing nature of this study, summary of Part 2 data will be strictly by patients initially randomized to active versus placebo patients that transition to active therapy. The groups will be labeled as BARD or PBO-BARD. All patients randomized to an active dose of bardoxolone methyl in Part 1 will be summarized with the BARD group in Part 2 analyses. All patients randomized to placebo in Part 1 will be summarized with the PBO-BARD group in Part 2 analyses.

Additional by-dose level results may be presented to explore long term trends by dose level, but will be included in an ad hoc manner.

### 3.5.2 Patient characteristics and exposure

Demographics and baseline disease characteristics will be summarized for patients who continue into study Part 2.

Exposure will be summarized using the Part 2 treatment groups (BARD, PBO-BARD) for the following:

- Total time in Part 2: ([last dose date] – [Week 16 visit date] + 1)
- Total time in study: ([last dose date] – [first dose date] + 1)

Discontinuations in Part 2 prior to study termination will be listed.

### 3.5.3 Concomitant Medications

The WHO Drug Dictionary will be used to classify all medications recorded during this study. The numbers and percentages of patients who had started taking any post-baseline concomitant medications during Part 1 (i.e., start date after study Day 1 through Week 16) or Part 2 will be summarized by medication for each treatment arm.

In the presence of partial dates, the available data (month and/or year) will be compared to the appropriate study reference dates to identify the most likely study period.

### 3.5.4 Efficacy

Efficacy analyses described in Section 3.4.3 will not be performed on available data from Part 2. Instead, 6MWD will be summarized using descriptive statistics only (include 95% confidence interval for change from baseline at each visit) using the Part 2 treatment groups (BARD, PBO-BARD) Patients randomized to placebo and converted to bardoxolone methyl in Part 2 should use the Week 16 eGFR value as baseline. If the Week 16 eGFR lab collection occurs after the date and time of first dose at Week 16, then the closest value prior to Week 16 should be used as baseline for patients randomized to placebo and converted to bardoxolone methyl. No inferential statistics will be provided for Part 2 data and missing 6MWD will not be imputed in Part 2.

#### 3.5.4.1 Part 2 Changes from Baseline in 6MWD

Due to the ongoing nature of this study, summary of Part 2 data will be strictly by patients initially randomized to active versus placebo patients that transition to active therapy. The groups will be labeled as BARD or PBO-BARD. All patients randomized to an active dose of bardoxolone methyl in Part 1 will be summarized with the BARD group in Part 2 analyses. All patients randomized to placebo in Part 1 will be summarized with the PBO-BARD group in Part 2 analyses.

In the Part 2 (open-label) portion of LARIAT, all active doses within a cohort will be pooled (including placebo patients randomized to active in Part 2). All active doses within a cohort, the BARD group, and PBO-BARD group will be compared to baseline 6MWD.

Actual values and changes from baseline will be summarized using descriptive statistics (including mean, standard deviation, quartiles, median, minima and maxima).

### 3.5.5 Safety

Safety analyses described in Section 3.4.4 will be performed on available safety data from Part 2 using the Part 2 treatment groups (BARD, PBO-BARD). Change from baseline summaries of safety described in 3.4.3 will include both change from baseline (Part 1) and change from the end of Part 1 (Week 16) for Part 2.

Analyses of adverse events will count only Part 2 treatment-emergent adverse events (TEAEs), defined as new or worsened events after the Week 16 visit. New or worsened events after Week 16 visit are those events with an AE start date after the Week 16 study visit, or previously recorded AEs with an adverse change in severity (e.g., went from mild to moderate or moderate to serious) after the Week 16 study visit. Similarly, only new onset concomitant medications (date of first dose after the Week 16 visit) will be included in Part 2 summaries.

Shift tables will be provided to assess changes from normal to abnormal shifts from Week 16 to each nominal visit for chemistry and hematology parameters.

Additional details will be provided in the mock Tables, Listings, and Figures.

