Treatment-compliant patients who have completed Part 2 of the study are eligible to continue receiving bardoxolone methyl through an extended access program (Study 402-C-1602). After Week 32, visits will occur every 24 weeks until bardoxolone methyl is available through the extended access program. Once bardoxolone methyl is available through the extended access program, patients in Part 2 who have completed at least 32 weeks of the study will complete an End of Treatment Visit.

Number of patients (planned):

Approximately 198 patients are expected to be enrolled in Part 1 of the study (38 patients in Cohort 1; 16 patients in Cohort 2; and approximately 24 patients in each of Cohorts 3a-b and 4a-d). Based on the variability in 6MWD observed in Cohorts 3 and 4, the Sponsor may choose to increase the number of patients to a maximum of 72 patients in each of Cohorts 3a-b and 4a-d. Variability for each subcohort will be assessed separately. The maximum number of patients enrolled will be 486.

All eligible patients from Part 1 will be included in Part 2, and no new patients will be randomized to Part 2 of the study.

Diagnosis and main criteria for inclusion:

1. Adult male and female patients ≥ 18 to ≤ 75 years of age upon study consent;
2. BMI > 18.5 kg/m²;
3. Symptomatic pulmonary hypertension WHO Functional Class II and III;
4. WHO Group I, III, or V PH according to the following criteria:
 - a. If diagnosed with WHO Group I PAH, then one of the following subtypes:
 - i. Idiopathic or heritable PAH;
 - ii. PAH associated with connective tissue disease;
 - iii. PAH associated with simple, congenital systemic-to-pulmonary shunts at least 1 year following shunt repair;
 - iv. PAH associated with anorexigen or drug-induced toxicity;
 - v. PAH associated with human immunodeficiency virus (HIV); or
 - b. If WHO Group III PH, then primary diagnosis must be one of the following subtypes:
 - i. Connective tissue disease associated ILD (CTD-ILD);

- ii. Idiopathic pulmonary fibrosis (IPF) according to the American Thoracic Society and European Respiratory Society (ATS/ERS) guidelines (Raghu 2011);
 - iii. Nonspecific interstitial pneumonia (NSIP) or the following idiopathic interstitial pneumonia subtypes, according to the American Thoracic Society and European Respiratory Society (ATS/ERS) guidelines (Travis 2013):
 1. Respiratory bronchiolitis-associated interstitial lung disease;
 2. Desquamative interstitial pneumonia;
 3. Cryptogenic organizing pneumonia;

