7. INVESTIGATIONAL PLAN

7.1. Overall Study Design

This study consists of two parts: a 16-week double-blind, randomized, placebo-controlled treatment period (“Part 1”), followed by an extension period (“Part 2”). All patients who complete treatment in Part 1 may continue to Part 2. Within Part 1, the study consists of a dose-ranging phase and a dose-titration phase. Qualifying patients with PH in both the dose-ranging and dose-titration phases will be followed for safety, tolerability, and efficacy, and all patients enrolled in the study will follow a similar schedule of assessments.

Part 1

Cohorts 1 and 2: In the dose-ranging phase of Part 1 of the study, up to two independently randomized cohorts may be opened at each dose level and patients will be allocated based on their baseline 6MWD (i.e., Cohort 1 for $6MWD \leq 450$ m and Cohort 2 for $6MWD > 450$ m). Once opened for enrollment, each dose group will include the next eight eligible patients randomized using a 3:1 assignment ratio (bardoxolone methyl:placebo) to be administered once daily for 16 weeks. Within each cohort type, patients will be enrolled to one dose group at a time.

A Protocol Safety Review Committee (PSRC) will assess the starting dose of 2.5 mg and each new dose level of bardoxolone methyl for safety and tolerability based on review of all available data for this study at the time of each review. PSRC reviews will occur after the Week 4 data are available for the first eight patients enrolled at each new dose level combined across both Cohorts 1 and 2. The PSRC assessment will include a dose level recommendation for subsequent dose groups to escalate to a higher dose, proceed to a lower dose, or maintain the current dose. The PSRC may also recommend stopping dosing for current cohorts. Upon completion of dose ranging, the PSRC will continue to meet at regular intervals (approximately quarterly) to monitor safety of all enrolled patients.

Data from all patients enrolled in Cohort 1 (≤ 450 m patients) and Cohort 2 (> 450 m patients) will be used to provide information regarding the optimal dose range for evaluation of safety, tolerability, and efficacy, allowing the sponsor to select an appropriate dose of bardoxolone methyl for further evaluation in patients with WHO Group I PAH. Selecting from PSRC-recommended dose levels, the sponsor will determine the dose level for each subsequent dose group.

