12.3. Statistical Analyses

A statistical analysis plan (SAP) detailing the analyses will be developed prior to the database lock. All statistical analyses and data summaries will be performed using SAS® (Version 9.1 or higher) or other similar software. The SAP will serve as the final arbiter of all statistical analyses. Data will be summarized overall using descriptive statistics. Continuous data will be summarized with number of patients (n), mean, median, minimum, maximum, standard deviation, coefficient of variation, and geometric mean (where applicable). Categorical data will be summarized using frequency counts and percentages.

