#### 3.4.5.1 Part 1 Treatment Emergent Adverse Events

The Medical Dictionary for Regulatory Activities (MedDRA) dictionary will be used to classify all adverse events reported during the study by system organ class (SOC) and preferred term

(PT). Analysis of treatment-emergent adverse events from Part 1 (Part 1 TEAE) will include all new or worsening adverse events with date of onset during or after the date of first study drug administration through the end of Part 1. Part 1 TEAE summaries will exclude adverse events with date of onset after the Week 16 visit date or date of onset more than 30 days after the date of last study drug administration for patients who discontinue treatment. Part 2 TEAE summaries will exclude adverse events with date of onset more than 30 days after the date of last study drug administration for patients who discontinue treatment. Adverse events will be summarized by SOC and PT. Tables and listings will summarize adverse events occurring in Part 1 and 2 separately. Drug-related AEs, SAEs, and serious drug-related AEs will be summarized accordingly. Multiple occurrences of the same event will be counted once for each patient at the level of SOC and the level of PT.

Adverse events by SOC, PT, and severity will also be summarized. Multiple occurrences of the same event will be counted once for each patient by preferred term under the highest severity.

In the presence of partial dates, the available data (month and/or year) will be compared to the appropriate study reference dates to identify the most likely study period.

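### Part 2 adverse events are counted once per patient over follow-up of unequal length, so the percentages depend on enrolment date and data cut

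*SAP*

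**What the plan says.** SAP 3.5.5 says that the Part 1 safety analyses "will be performed on available safety data from Part 2 using the Part 2 treatment groups (BARD, PBO-BARD", that is, by patients first randomised to active drug (BARD) and patients who cross over from placebo (PBO-BARD). It cites Section 3.4.4 for those analyses; in the body of the SAP they stand in 3.4.5. The counting rule is in SAP 3.4.5.1: "Multiple occurrences of the same event will be counted once for each patient at the level of SOC and the level of PT". The Part 2 event window opens after Week 16: "Analyses of adverse events will count only Part 2 treatment-emergent adverse events (TEAEs), defined as new or worsened events after the Week 16 visit". For patients who discontinue, SAP 3.4.5.1 closes it 30 days after the last dose. Protocol 12.3 gives the general form of summary: "Categorical data will be summarized using frequency counts and percentages".

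Part 1 has a fixed length, being "a 16-week double-blind, randomized, placebo-controlled treatment period". Part 2 does not. The Protocol synopsis and 7.1 say "After Week 32, visits will occur every 24 weeks until bardoxolone methyl is available through the extended access program", and a patient must reach Week 32 before leaving by that route.

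SAP 1.8 and 3.5 pool patients for Part 2 safety. The first pool is "All PAH patients (Cohorts 1, 2, 3a, and 3b patients"; the others are CTD-PAH, non-CTD PAH and Cohort 4. SAP 3.5.2 summarises total time in Part 2 by group but does not link it to adverse events. No section gives exposure-adjusted rates, interval tables or a common cut-off for Part 2 events.

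**The concern.** The percentage of patients with at least one event rises with time observed, even when the underlying rate is the same. Part 2 time is set largely by when a patient enrolled and when the data are cut. SAP 1.9 and 1.9.4 let the sponsor analyse accumulating Part 2 data at times of its choosing, including for regulatory interactions, so the same table will show different percentages at each cut.

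Two features add to this. Scheduled contact thins sharply after Week 32, so late person-time is observed less closely. And the PAH pools combine an earlier phase randomised 3:1 with a later phase randomised 2:1, so the two Part 2 columns are expected to mix long and short follow-up in different proportions. These tables are part of the totality of information on which SAP 1.5.2 rests the dose-range judgement.

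**Working it through.** **Check of cohort sizes (Protocol 7.2).** 38 + 16 + 6 × 24 = 198 and 38 + 16 + 6 × 72 = 486. Both match the stated totals. The documents give no event rate or follow-up figure for Part 2, so those inputs below are assumptions.

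**Length of Part 2.** The minimum for a completer is Week 16 to Week 32, or 16 weeks. The maximum uses the synopsis dates (January 2014 to December 2018), less 16 weeks of Part 1 and 4 weeks of follow-up: about 232 to 241 weeks. The ratio is about 15 (232/16 = 14.5; 241/16 = 15.1). This is an upper bound, because the opening date of the extended access program is not given.

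**Scheduled contacts after Day 1 with adverse event collection (Protocol Tables 3 to 6).**

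| Period | Cohorts 1-2 | Cohorts 3-4 |
|---|---|---|
| Part 1, 16 weeks | 9 (13.5 per 24 weeks) | 13 (19.5 per 24 weeks) |
| Weeks 16-32 | 5 (7.5 per 24 weeks) | 9 (13.5 per 24 weeks) |
| After Week 32 | 1 per 24 weeks | 1 per 24 weeks |

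Scheduled contact after Week 32 is about 14 to 20 times sparser than in Part 1.

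**Effect of time alone.** Assume a constant hazard: share with an event = 1 − exp(−rate × weeks/52.18). At 0.2 per patient-year this is 5.9% over 16 weeks, 34.9% over 112 weeks and 59.5% over 236 weeks. The rate is the same each time.

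**Mix of phases in the All PAH pool.** Assume that all patients continue into Part 2.
- Cohorts 1-2: 54 at 3:1 gives 40.5 active and 13.5 placebo.
- Cohort 3 at planned size: 48 at 2:1 gives 32 and 16. Early share: 40.5/72.5 = 55.9% of BARD, 13.5/29.5 = 45.8% of PBO-BARD.
- Cohort 3 at maximum: 144 at 2:1 gives 96 and 48. Early share: 40.5/136.5 = 29.7% and 13.5/61.5 = 22.0%.

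**Spurious difference.** With the same rate in every patient, BARD minus PBO-BARD = (difference in early share) × [exp(−rate × late time) − exp(−rate × early time)]. Assumed mean Part 2 follow-up in years (early, late) is (2, 1), (3, 1) or (3, 0.6). Assumed rates are 0.2, 0.4 and 0.8 per year.

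| Cohort 3 size | Smallest: (2, 1), rate 0.2 | Largest: (3, 0.6), rate 0.8 |
|---|---|---|
| 48 | 0.101 × (0.819 − 0.670) = 1.5 points | 0.101 × (0.619 − 0.091) = 5.3 points |
| 144 | 0.0772 × (0.819 − 0.670) = 1.1 points | 0.0772 × (0.619 − 0.091) = 4.1 points |

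In Cohort 4 every subcohort is 2:1, so the shares do not differ between groups and the formula gives zero. The same holds within any single cohort.

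**Denominator for a rate.** Total time in Part 2 (SAP 3.5.2) ends at the last dose, while events in patients who discontinue count for 30 more days. A patient who stops at Week 32 has about 16 × 7 = 112 days of exposure but 142 days at risk (142/112 = 1.27). Using the SAP quantity unchanged would overstate rates most where follow-up is shortest.

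**The case against.** The case against is substantial, and much of it stands.

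- A reader might infer that BARD and PBO-BARD differ in follow-up throughout. They do not by design: patients within a cohort are randomised together and share a calendar and schedule. Only PAH pools that mix 3:1 and 2:1 cohorts are affected. SAP 3 also says that all analyses are presented by cohort. That sits uneasily with the pooling in 1.8 and 3.5, where individual-cohort summaries are added only for eGFR, the walk test and lung function.
- A reader might infer that BARD will look worse. Protocol 5.1.2 to 5.1.4 describes fluid overload risk in the first three to four weeks, transaminase peaks at two to four weeks, and muscle spasms mostly in the first two months. PBO-BARD patients meet that period in Part 2; BARD patients have passed it. This works against a BARD excess, and a constant hazard fits such events poorly.
- A reader might infer that the plan compares Part 1 with Part 2. It does not: "Tables and listings will summarize adverse events occurring in Part 1 and 2 separately". Part 2 has no inferential statistics and no cumulative summaries (SAP 3.5.4, Appendix B).
- One contact per 24 weeks is the current scheduled minimum. SAP 3.7.3 shows that visits past Week 32 changed between protocol versions, and patients may volunteer events at any time (Protocol 9.10.17).
- SAP 3.5.2 makes unequal exposure visible. Table detail is partly left to mock tables that are not available here, and percentages for adverse events are inferred from Protocol 12.3.

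These points limit the size and reach of the problem. They do not supply a denominator or a common window, and a separate exposure table does not let a reader adjust individual terms.

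**Conclusion.** The point holds as a minor one. Once-per-patient percentages over an open-ended Part 2 depend on enrolment date and data cut, and cannot be read against the 16-week Part 1 figures. In the mixed PAH pools BARD is expected to have somewhat longer follow-up. Under the assumed rates and follow-up the artefact is roughly 1 to 5 points: 1.5 to 5.3 at planned size, 1.1 to 4.1 if Cohort 3 reaches 144. That rests on a constant hazard, no dropout, Cohorts 1 and 2 enrolling before Cohort 3, and follow-up means that the documents do not give. The CTD and non-CTD pools cannot be sized, because the CTD split within Cohorts 1 and 2 is not stated. The net direction for a given event is uncertain. The documents do not support a claim of bias in every Part 2 comparison.

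**What to change.** In SAP 3.5.5, keep the planned counts and add:

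1. Part 2 treatment-emergent and serious adverse events for the fixed Weeks 16-32 window, which every continuing patient is scheduled to complete and which captures the first 16 weeks on drug in PBO-BARD.
2. Exposure-adjusted incidence per 100 patient-years, separately for Weeks 16-32 and after Week 32. Time at risk should match the event window, running to the last dose plus up to 30 days for patients who discontinue, rather than the total time in Part 2 defined in SAP 3.5.2.
3. For the PAH pools, both of these shown by Cohorts 1-2 and Cohort 3.

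The cost is SAP wording and a few extra table columns; the dates are already collected. The drawback is that each rate averages over a hazard that is probably not constant, which the split at Week 32 only partly relieves.

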## 3.6 Pharmacokinetic Analysis

A separate document contains details regarding the planned pharmacokinetic analyses.

## 3.7 Missing and Partial Data

For the analysis of safety variables, partial dates may be imputed; otherwise, missing data will be treated simply as missing. However, if an AE onset date is missing, it will be imputed (see Appendix C). The algorithms for imputation of partial dates depend upon the parameter (see Appendix C). The central laboratory uses assays that have lower limits of detection (LLD). Continuous laboratory data results which are less than the lower limit of detection or above the upper limit of quantification will be imputed to the value of the lower or upper limit plus or minus one significant digit, respectively (e.g., if the result of a continuous laboratory test is  $< 20$ , a value of 19 will be assigned).

Imputation for missing efficacy data (i.e., 6MWD) is described with the efficacy analysis Section 3.4.4.

### 3.7.2 Analysis Windows for Part 1

For all Part 1 analyses of 6MWD, scheduled visits will be used regardless of study day, as well as any unscheduled or end of treatment visits within the visit windows listed in Section 3.7.4. If an unscheduled or EOT visit falls within the same window as a nominal study visit, the average of the two will be used. For subjects that prematurely discontinue treatment before Week 16 with a 6MWT recorded at the End of Treatment (EOT) assessment, that EOT 6MWD will be used in analysis for the nominal protocol visit most closely matching the subject's visit schedule.

For all other Part 1 efficacy and safety analyses, if multiple assessments fall within the same analysis visit, the assessment closest to the target study day specified in the protocol will be used. If two assessments are equidistant from a post-baseline target visit day, the earlier assessment will be used. Visits that do not occur in all versions of the protocol (i.e., Week 6) should be treated as unscheduled assessments.

### 3.7.3 Analysis Windows for Part 2

Part 2 assessments will be used in efficacy and safety analyses if the assessment was collected within the scheduled window below. Study day will be calculated for each assessment and compared to the protocol defined study day for each visit. In general, analysis in Part 2 will be defined as follows:

